#### Measuring outcome indicators

#### Primary outcome: Helminth infection at 12 months after deworming

This will be determined through a cross-sectional survey conducted in intervention and control arms at 12 months after the baseline survey (Figure 2). (The baseline survey is required to identify and treat students who were still infected in spite of the initial deworming, and to generate data about potential imbalances between trial arms at the beginning of the follow-up period, in order to facilitate adjustments in the data analysis). A questionnaire will be administered to collect information on age, sex, school grade, number of family members, personal risk factors potentially associated with STH, including last time hands were washed with/without soap or soil-eating behaviours, materials used for anal cleaning after defecation (Freeman 2013), and information about potential confounding variables related to the environment, including availability of water at home, hand-washing behaviours at home, source of food eaten etc. Study ID-numbers will be assigned and stool samples will be collected and processed as described below.

## Stool sample collection:

Pre-labelled 50 ml sample bottles will be distributed in the school and the fresh stool samples collected on the next day. Each student participating in the study will receive an individual container labelled with the unique ID number and the individual's name. On distribution of the sample containers the interviewer will explain how the containers should be used. Using a leaflet, the purpose of the stool examination will be explained and parents/ guardians will be asked to help their children with sample collection. In the schools, when the filled sample containers are returned, the stool samples will be stored on ice in a cool box and brought to the laboratory for analysis as soon as possible.

The prevalence and intensity of intestinal nematode infections (in particular; *Ascaris lumbricoides,* and *Trichuristrichuria,* but also hookworm) and the prevalence of protozoa infections (in particular; *Giardia intestinalis*) will be determined.

All study participants who have a positive stool sample (in spite of the general deworming treatment just days before the baseline survey), will be provided with anthelmintic or anti-protozoal medication according to the lab results obtained. The same will apply to participants with positive samples at the endlinesurvey.

## Laboratory methods: helminth and protozoa analysis

We will use the formol-ether concentration method to identify helminth ova and protozoa cysts, and to determine infection intensity. On the day of collection, stool samples will be fixed in 10% formalin in the field laboratory. On arrival at the parasitology laboratory of NIMR Mwanza centre, the samples will be classified based on their consistency as either F(ormed), S(oft), L(oose) or W(atery).

The formal-ether concentration technique will be used for analysis, as it has consistently shown higher recovery, especially in light infections, in comparison to other techniques (Young 1979). For safety reasons, ether will be replaced by ether-acetate, which has been shown not to affect the results (Ridley 1956).

Intensity (as eggs per gram) of intestinal nematode infections will be quantified by taking a pre-weighted stool sample of approximately 2 grams, which will be dissolved in 6 ml of formalin (30% formaldehyde). After proper mixing, this will be transferred to a glass tube in which 2 ml of ether-acetate will be added. The tubes will be centrifuged at 2400 rpm for two minutes, after which fat and formal water

will be drained off. All residues in the tube will be analyzed in a saline solution under a 10 by 10 magnification for helminth eggs. A sample will be declared negative if 3 slides yield no ova. Intensity of infection will be determined by both egg counts and infection intensity categories (i.e. light, moderate, heavy).

## Secondary outcome: hand-washing behaviours

Hand-washing behaviours will be assessed by direct, structured observation in schools, and by self-reports asked of students in schools regarding both home and school-based behaviours. Observations will be conducted by trained monitors who will anonymously record whether students wash their hands and make use of soap, after using a toilet. The percentage of students washing hands with / without soap will be determined.

Hand washing behaviours at home will be assessed based on students' self-reports. For these self-reports simple questionnaires will be administered to students themselves (whilst in school).

Self-reported hand-washing behaviour is subject to recall bias, but also desirability bias. We will therefore collect this information using techniques that minimises desirability bias (e.g. we will not ask whether a participant washed hands, but how often s/he could not do so because of time pressure or other external factors).

## Secondary outcome: intensity of worm infections

The intensity of worm infections will be graded, and will be recorded during the microscopic assessment of all stool samples as described above in the section on laboratory methods.

## Secondary outcome: Levels of hand contamination

Data on hand contamination is scarce, especially for the presence and concentration of STH ova, and no data on variations between individuals, or for particular risk factors has been found in the literature. A required sample size is therefore difficult to estimate. We plan to sample hand-rinse water from 20% of the study population of the endline survey (about 640 children in total), and will analyse hand-rinse samples for the presence and concentration of STH ova (and if funds permit also for the presence of *Escherichia coli bacteria*. Additional funding is currently being sought for this purpose).

Again a short questionnaire will be administered to collect information on age, sex, last time the student went to the toilet to defecate, last time hands were washed with/without soap, and also on activities performed during the day that may have led to the contamination of hands with faecal material.

The number of ova on hands will be assessed through a concentration technique using McMaster slides and developed under the first phase of SHARE (Jeandron 2014). A 100 ml sample from the hand rinse wash water will be used for the detection of STH ova and (funds permitting) of *Escherichia coli bacteria*. Results from hand rinses will be compared between schools across the trial arms, and also with

the individual infection status determined from the stool analysis conducted at about the same time.

#### Cost and cost-effectiveness study

For the costing study, the expenditures made for the design and implementation of the intervention will be documented. Investment costs (development of educational materials; training of teachers) and intervention running costs (pre-intervention worm infection survey, feedback meetings with parents, distribution of leaflets, class-room sessions, provision of hardware such as soap and soap-dispensers, monitoring of intervention in schools, etc.) will be itemised separately. For the costing exercise we will use the ingredients approach. Costs will be documented in US dollars at 2016 prices.

Care will be taken to not include research costs (e.g. baseline and FU evaluation surveys). Costs of the deworming campaign in all schools and worm treatments provided in all schools to infected students following the baseline and endline surveys will also be documented but are not a component of the hand-washing intervention and will not be included in the cost-effectiveness analysis.

For the cost-effectiveness study we will relate the expenditures incurred for the intervention (incremental costs of the intervention over and above that of deworming campaign) to the average number of additional infections prevented due to the intervention over and above those cured due to the deworming campaign (incremental intervention effects). The cost-effectiveness will be expressed as costs per infection prevented.

This work will be conducted by MITU's health economist in collaboration with the Ifakara Health Institute (IHI).

#### **STUDY LIMITATIONS**

The main outcome indicator (prevalence of STHs at the endline survey in the two arms of the trial) is subject not only to the desired intervention (hand-washing behaviour) but also to infections from other sources, and may be modified by environmental and other confounding factors as described further above. Such factors will therefore be carefully documented und used for adjustment in the analysis, but residual confounding may occur. Should the intervention trials how a null-result it will be important that the study can disentangle the reasons: whether the hand-washing intervention has been unsuccessful, or whether other sources of infection may have played a role that may have overridden any intervention effects. Also for this reason, we will conduct the sub-study on hand contamination with helminth eggs described above.

We are aware that even after correct repeat deworming with Albendazole, some children may still be infected, particularly with trichuriasis; and that not all infections will be detected by the stool microscopy-based laboratory technique to be used, particularly lighter infections. However this fact does not invalidate the annual deworming campaigns or jeopardise the validity of the intervention trial: incomplete eradication of helminth infection or misclassification of light infections would occur in both arms of the trial; and their consequence would be a gradual dilution of the measurable intervention effect.

The proposed stool microscopy method for the detection of helminth infections has a lower sensitivity than a polymerase chain reaction (PCR) method. However, the proposed methodology will be sufficient for the purpose of this randomised trial for which the outcome is helminth infection *prevalence* rather than an accurate diagnosis of infection at individual level.

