### **Evaluation of the intervention**

#### Overview

The intervention will be evaluated through a cluster randomised controlled trial. Sixteen primary schools will be randomised to receiving the above intervention package (N=8) or to be in the control arm (N=8).

Whilst the intervention will be delivered to all classes 1 - 6 of the schools randomised to the intervention arm, a random selection of classes will be recruited for the evaluation. For the evaluation, we will select an equal number of classes in both arms, and the random selection will be restricted so that selected classes represent comparable age bands (to avoid that by chance there would be more 'younger' classes in one of the trial arms than in the other). The target group will be children aged 6 - 12 years, but all children in the participating classes will be enrolled, including those that may fall outside of this age band.

The evaluation will involve two cross-sectional surveys: a baseline survey (conducted just after the deworming campaign in both arms of the trial, and just after the intervention has been started in the intervention arm); and an endline survey to be conducted about 12 months after the baseline survey in each respective school (Figure 2).

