## Outcomes

The primary outcome will be the combined prevalence of ascariasis and trichuriasis in students' stool samples in both intervention and control schools determined at about 12 months after initial deworming in both intervention and control schools.

Secondary outcomes will include

- (i) hand-washing behaviour in schools (reported and observed) and at home (reported only)
- (ii) intensity of ascariasis and trichuriasis infections at baseline and 12 months after deworming
- (iii) levels of hand contamination with worm eggs and E. coli bacteria at 12 months after deworming

(iv) prevalence and intensity of hookworm infection at baseline and at 12 months after deworming

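### Home hand-washing, which the intervention sets out to change, is listed as a confounder to be adjusted for in the analysis of the main outcome

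*Protocol*

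**What the plan says.** Two passages of the protocol have to be read together.

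- The STUDY LIMITATIONS section says that the main outcome, endline prevalence, "may be modified by environmental and other confounding factors as described further above". It continues: "Such factors will therefore be carefully documented und used for adjustment in the analysis".
- The primary-outcome section under Measuring outcome indicators contains the only earlier list of confounders. The questionnaire is to collect "potential confounding variables related to the environment, including availability of water at home, hand-washing behaviours at home, source of food eaten etc". A separate group in the same sentence, labelled personal risk factors, includes "last time hands were washed with/without soap or soil-eating behaviours" and anal-cleaning materials.

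Three other places show what role home hand-washing plays in this trial.

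- Under Intervention components, the parents' meeting is meant to improve children's hygiene at home as well as at school.
- Under Outcomes, the first secondary outcome is hand-washing in schools and, by self-report, at home.
- STUDY LIMITATIONS itself equates hand-washing behaviour with the intervention, just before it commits to adjustment.

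On timing, the questionnaire is described under the endline survey: "This will be determined through a cross-sectional survey conducted in intervention and control arms at 12 months after the baseline survey". The baseline survey takes place "just after the intervention has been started in the intervention arm" (Overview, under Evaluation of the intervention).

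**The concern.** The protocol gives one variable three roles: part of the mechanism, an outcome, and a confounder to be adjusted away. In a randomised comparison, a variable that allocation changes and that in turn affects infection is a mediator. Conditioning on it removes whatever part of the benefit travels through it, so the more the package works through hand-washing at home, the more of its effect is taken out.

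The aim of the trial and its sample size both concern the effect of the whole package. An analysis that followed these two passages would answer a different question. It could also mislead the planned reading of a null result. STUDY LIMITATIONS proposes to attribute a null either to failed hand-washing or to other sources of infection, but an adjusted null could come from the adjustment itself, and then neither explanation would be right.

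**Working it through.** **1. Is home hand-washing among the factors to be adjusted for?** STUDY LIMITATIONS points back to confounding factors described earlier. Only the primary-outcome measurement section lists any, and it uses the same label. Home hand-washing is in that list. Nothing in the protocol excludes it or limits adjustment to variables fixed before allocation.

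**2. Could a version measured before the intervention be used?** No. The questionnaire belongs to the endline survey. Even the baseline survey follows deworming, and by the schedule under Intervention components the parents' meeting and the first classroom session both come before deworming.

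**3. Reproduce the planned power.** Inputs from Sample size considerations: p0 = 0.30, p1 = 0.18, m = 200 pupils per school, k = 0.3, c = 8 schools per arm. Two-sided alpha is taken as 0.05; Table 1 prints 0,95 under type-1 error, and 0.05 reproduces the chosen design. The Hayes-Bennett formula is

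c = 1 + (z_α/2 + z_β)² × V / (p0 − p1)², with V = p0(1−p0)/m + p1(1−p1)/m + k²(p0² + p1²).

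- V = 0.00105 + 0.000738 + 0.09 × 0.1224 = 0.012804.
- c = 1 + 7.849 × 0.012804 / 0.0144 = 7.98, so 8 per arm, as stated.
- Power at c = 8: Φ(√(7 × 0.0144 / 0.012804) − 1.96) = Φ(0.846) = 80.1%.
- For 30% against 15% at 95% power the formula gives 7.82, again 8 per arm.

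The stated design therefore reproduces, and it is a design for the total effect, ratio 0.60.

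**4. What would remain after adjustment, with error-free measurement?** Let s be the share of the log effect that passes through the adjusted variable. The protocol does not give s, so a range is assumed. The remaining ratio is 0.60^(1−s). Power is the step 3 formula at c = 8 with p1 = 0.30 × ratio. This treats the remaining contrast as a simple two-arm comparison and ignores any change in variance due to adjustment.

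| s (assumed) | remaining ratio | p1 equivalent | power |
|---|---|---|---|
| 0 | 0.60 | 18.0% | 80.1% |
| 10% | 0.63 | 18.9% | 72% |
| 25% | 0.68 | 20.5% | 58% |
| 50% | 0.77 | 23.2% | 31% |
| 75% | 0.88 | 26.4% | 11% |
| 100% | 1.00 | 30.0% | 2.5% (beneficial direction) |

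**5. What does misreporting do?** The simulation used 16 schools of 200 pupils, a school-level risk factor with mean 1 and SD 0.3, true total ratio 0.60, and assumed home hand-washing of 30% in control and 80% in intervention schools. Poisson regression was fitted without and then with the hand-washing variable, 100 runs per cell. Entries are unadjusted → adjusted ratio.

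| share mediated | no error | 20% misclassified | 35% misclassified |
|---|---|---|---|
| all | 0.622 → 1.034 | 0.603 → 0.700 | 0.599 → 0.620 |
| half | 0.593 → 0.765 | 0.596 → 0.643 | 0.585 → 0.595 |
| about a fifth (indirect ratio 0.9; ln 0.9 / ln 0.6 = 0.21) | 0.617 → 0.686 | 0.596 → 0.616 | 0.597 → 0.602 |

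The scatter of the unadjusted values around 0.60 is simulation noise. The shift is towards 1 in every cell and shrinks quickly as self-report gets worse. The simulation contains no unmeasured common cause of hand-washing and infection.

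**The case against.** The strongest reply is that the protocol fixes no model. The adjustment sentence stands in a limitations section, names no covariate, and speaks of the analysis in general. Project management and governance leaves the analysis to a protocol agreed before analysis begins. The limitations paragraph also contrasts hand-washing with other sources of infection, so the factors to be adjusted for could be read as everything except hand-washing.

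Part of this stands. A reader might infer that the primary analysis is fixed to adjust for hand-washing. The protocol never says so, and a later plan could drop the variable. A reader might also infer that every behaviour on the questionnaire is to be adjusted for. Among the behaviours cited, only home hand-washing carries the confounder label; the last hand-wash, soil-eating and anal-cleaning materials are called personal risk factors, and observed school hand-washing is not in the list.

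The reply does not remove the problem. The contrast in the limitations paragraph still refers back to an earlier description, and the only one available classifies home hand-washing as a confounder. Deferring detail to a later plan does not correct a wrong classification; a plan that followed the protocol faithfully would inherit it.

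The objection to size is also fair. Ratios of 0.77 or 1.00, and power of 31%, need a large mediated share and error-free reporting. The protocol itself warns of recall and desirability bias in self-reported hand-washing.

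**Conclusion.** The point holds in a limited form. The protocol labels home hand-washing a confounder and commits to adjusting for such factors in the analysis of the main outcome. By the protocol's own account the variable is an intervention target and a secondary outcome, and it is measured only after the intervention has started. Adjusting for it would not estimate the total effect for which the trial is sized, and the expected direction of the shift is towards no effect.

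The size cannot be derived from the protocol. With error-free measurement and an assumed mediated share of 10% to 100%, a true ratio of 0.60 becomes 0.63 to 1.00. With 20% misclassification and full mediation it becomes about 0.70, and with 35% about 0.62. Unmeasured factors that affect both hand-washing and infection could add bias in either direction, so attenuation is the expected result and not a certain one. The documents do not support a claim that the trial will report a working intervention as failed.

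**What to change.** Two changes of wording, plus a home for the variables removed from adjustment:

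- In the primary-outcome measurement section, delete home hand-washing from the list of potential confounders.
- In STUDY LIMITATIONS, state that adjustment of the main between-arm comparison is limited to covariates the intervention cannot change, for example age, sex and class.
- Analyse hand-washing, and any other questionnaire behaviour the intervention could change, only in a separately labelled process or mediation analysis that does not feed the main estimate.

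The new text should not require stratification factors or school prevalence before the trial. The protocol describes no stratified randomisation, and its worm survey before the intervention covers intervention schools only.

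The cost is an edit to two sections. The questionnaire, the surveys and the 16 schools stay as they are, because the sample size was already calculated for the total effect. The change should be made before the analysis plan is agreed.

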## Timelines and sequence of events

The overall project will take 2 years and 9 months, which includes the preparation phase (not part of this protocol) and the controlled trial (subject of this protocol).

With regards to the trial, the time from the introduction of the intervention in an intervention school to the end of the endline worm infection survey in the same school will take about 1 year and 3 months (Figure 2).

[figure not shown]
Because the project cannot be delivered simultaneously in all schools it will be phased in over a period of 3 - 4 months (Figure 3).

Data sets from the evaluation surveys will become available over time, and will be complete for the last schools enrolled about 1 year and 4 months after beginning of the trial.

Analysis of data will take about 4 months.

This protocol covers the main trial (i.e. the work to be done after completion of the formative work. The trial is expected to begin in July 2017, and data analysis to be completed by December 2018 (Figure 3).

# Figure 3 Phased project implementation

## ETHICAL CONSIDERATIONS

*Ethical clearance and supervision:* The study protocol has been approved by the SHARE Programme Executive Group. The study protocol, questionnaires, information sheets and consent forms for survey participants will be submitted to the ethical review committees at NIMR Tanzania and LSHTM for clearance. The study will be supervised by a Study Steering Committee (TSC).

*Study implementation:* The intervention will be offered to all students in the intervention arm. Because hygiene education and hand-washing after defecation and before meals are no invasive procedures, consent or assent will not be required for the intervention. In order to enrol students for the *evaluation surveys*, students will be asked for informed assent, and parents or guardians will be asked to provide informed consent based on a circulated information leaflet, and using an opt-out strategy for those who would not wish their children to participate.

Data collected from or about study participants will be treated with strict confidence. Names of study participants will be recorded so that they can be traced for follow up if required, but will be detached from clinical and other personal data. Students infected with STHs will be treated on the spot, students with other apparent ailments will be referred to local health units where they will be managed to the standard of care in accordance with current national guidelines.

The deworming campaign will be conducted in all participating classes according to standard guidelines of Tanzania. The campaign will conducted through the project but will imitate the deworming campaigns usually delivered by the MoHSW at regular intervals. After the baseline and endline surveys, any students with a current worm infection will receive treatment according to national guidelines.

